Official Study Title: Investigating the Cardiovascular Toxicity of Exposure to Electronic Hookah Smoking

Document Title: Statistical Analysis Plan

NCT Number: 03690427

Document Date: Original IRB Approval Date November 6, 2018

Statistical Analysis Plan for Endothelial Function

Statistical analyses were performed using SAS (version 9.4). Data were analyzed by the Shapiro–Wilk test to determine distribution. Once normality was demonstrated, we tested within-participant pre- versus post-exposure changes using paired t tests. For non-normally distributed variables Wilcoxon signed-rank test was used. We applied paired t tests to compare the pre- versus post-changes induced by ascorbic acid versus e-hookah vaping for variables that were normally distributed, and Wilcoxon signed-rank test for non-normally distributed variables. Data are expressed as mean \pm SE. Data for plasma nicotine, exhaled carbon monoxide, and flow-mediated dilation normalized for shear were not normally distributed and were additionally expressed as median (interquartile range). Statistical significance was set at the 0.05 level.

Statistical Analysis Plan for Central Arterial Stiffness and Biomarkers of Oxidative Stress and Inflammation

Paired Student *t* tests were used to compare continuous variables between sessions before and after exposure. Because of the crossover study design, we used a general linear model approach for repeated measures to examine differences between e-hookah and traditional combustible hookah; the models included two within-subject factors (product type and time point relative to exposure session), and the sequence of type of product exposure was included as a between-group factor. The effect of primary interest was the interaction between the two within-subject factors, product type and time point relative to the exposure session. Effect sizes are for the interaction of product-by-time point relative to exposure in the general linear model repeated-measures analysis and translated from eta-square metric to d-metric. Statistical significance was set at 0.05 and analyses were conducted using SPSS Statistics version 24.0 software (IBM).

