Official Study Title: Investigating the Cardiovascular Toxicity of Exposure to Electronic Hookah Smoking

Document Title: Study Protocol

NCT Number: 03690427

Document Date: Original IRB Approval Date November 6, 2018

Study Protocols for Vaping and Smoking Exposure Sessions:

E-Hookah Vaping Protocol. To determine the acute effect of e-hookah vaping on FMD, blood pressure, heart rate, and FMD were measured before and after (within ≤10 minutes) 30 minutes of e-hookah bowl vaping. Ten minutes after FMD testing (to allow arterial diameter to return to baseline size), endothelium-independent dilatation was assessed by administering sublingual nitroglycerin. Using an e-hookah bowl (Starbuzz Wireless E-head) placed on a traditional waterpipe, subjects were instructed to vape e-hookah fruit-flavored liquid containing 50/50 blend of propylene glycol and vegetable glycerin and 6 mg/mL nicotine, according to the package label (Starbuzz Tobacco, Inc.).

Traditional Charcoal-Heated Hookah Smoking Protocol. A traditional water-pipe was used for hookah smoking protocol. Participants were instructed to smoke the most popular brand of maassel cited by hookah smokers and manufactured in the United States (5%-10% tobacco fermented with molasses, fruit, and glycerin; Starbuzz Tobacco, Inc.) heated with two charcoal briquettes (Coco Nara 100% Natural Coal, Coco Nara).

To mitigate the impact of carryover effects, both exposure sessions were separated by a minimum of a 7-day washout period. Topography were standardized in accordance with hookah smoking puffing parameters observed in natural settings. Thus, for the duration of the 30-min inhalation sessions, all participants were cued verbally to inhale a 3-s puff at 20-s intervals, with vapor remaining in the lungs for approximately 3 s of breath-holding after inhalation. Supervision was carried out to prevent superficial vaping or hyperventilation. Experimental sessions took place in a specifically designed

smoking/vaping area, housed within the University of California, Los Angeles, Clinical and Translational Research Center.

Study Protocol for Flow-Mediated Dilation and Vascular Endothelium-Independent Dilation

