Study Protocol for Intravenous Ascorbic Acid Protocol. To determine if oxidative stress plays a mechanistic role in the e-hookah vaping-associated decline in FMD, the acute effects of e-hookah vaping on FMD and exposure biomarkers were assessed before and after intravenous administration of a supra-physiological dose of ascorbic acid (Mylan Institutional Inc.): priming bolus of 0.06 g per kg fat-free mass dissolved in 100 mL of saline infused at 5 mL min⁻¹ for 20 minutes followed by an intravenous infusion of 0.02 g per kg fat-free mass dissolved in 30 mL of saline administered over 60 minutes at 0.5 mL min⁻¹. The maximum dose of ascorbic acid administered did not exceed 5 g. Ten minutes after FMD testing, endothelium-independent dilatation was assessed by administering sublingual nitroglycerin (0.15 mg) with brachial artery images recorded continuously for 10 minutes.

Study Protocol for Central Arterial Stiffness

Carotid-femoral PWV was measured by simultaneous waveform capture using both a thigh-specific cuff and carotid artery applanation tonometry (SphygmoCor XCEL; AtCor Medical). Velocity ($dsf - dsc$ (m) / time (s)) was calculated by measuring the time difference between the initial upstroke of the recorded waveforms at each site. The linear distance was measured manually from the suprasternal notch to the top of the thigh cuff at the center line of the leg, at the location of the femoral artery (dsf), and subtracting the distance from the suprasternal notch to the location of the carotid pulse (dsc). The transit time between the carotid and the femoral pulse waves was determined automatically by the SphygmoCor software.

The augmentation index was derived from the contour of the brachial BP waveform. The brachial-artery waveform, calibrated using oscillometric brachial artery BP, was analyzed by the validated brachial-to-aortic SphygmoCor transfer function to generate a central waveform and associated parameters. The augmentation index was calculated as the ratio of augmentation pressure (difference between the second and first systolic peaks of the aortic pressure waveform) and pulse pressure expressed as a percentage.

Study Protocol for Biomarkers of Oxidative Stress and Inflammation

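### Should FMD also have been analysed with the product-by-time crossover model that the SAP uses for stiffness and biomarkers?

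*SAP*

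**What the plan says.** The SAP has two analysis sections, and they treat the design differently.

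- **Endothelial function (SAS).** "Once normality was demonstrated, we tested within-participant pre- versus post-exposure changes using paired t tests". Signed-rank tests replace these where normality fails. The only comparison between conditions is this: "We applied paired t tests to compare the pre- versus post-changes induced by ascorbic acid versus e-hookah vaping". The section has no e-hookah versus charcoal contrast and no sequence term. It also reports that "flow-mediated dilation normalized for shear were not normally distributed".
- **Central arterial stiffness and biomarkers (SPSS).** "Because of the crossover study design, we used a general linear model approach for repeated measures to examine differences between e-hookah and traditional" combustible hookah. In that model "the sequence of type of product exposure was included as a between-group factor", and "The effect of primary interest was the interaction between the two within-subject factors, product type and time point relative to the exposure session".

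The protocol gives two purposes for measuring FMD. Under E-Hookah Vaping Protocol it is "To determine the acute effect of e-hookah vaping on FMD". Under the intravenous ascorbic acid heading it is "To determine if oxidative stress plays a mechanistic role in the e-hookah vaping-associated decline in FMD". The paragraph on traditional charcoal-heated hookah describes the pipe, tobacco and charcoal and names no outcome.

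**The concern.** The SAP justifies its product model by the design, not by the outcome. If participants had FMD measured around both exposures, the same justification would cover FMD, yet the SAP gives no reason for leaving it out.

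What would be at stake is any statement that the two products differ, or do not differ, in their effect on FMD. Such a statement could then rest only on two separate pre/post p-values, which do not test a difference. An unadjusted paired comparison of the two changes would also be open to period effects if the two sequences were unequal in size. The data might already be in hand and the model is already in the SAP, so the addition looks almost free.

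**Working it through.** **1. Aims against tests.** The documents give no sample size, SD, correlation or sequence split, so there is no stated figure to reproduce. The main check is textual.

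| FMD aim in the protocol | Test in the SAP | Match |
|---|---|---|
| Acute effect of e-hookah vaping | Paired t or signed-rank, pre versus post | Yes |
| Role of oxidative stress in the e-hookah effect | Paired t or signed-rank on changes, ascorbic acid versus e-hookah vaping | Yes |
| E-hookah versus charcoal hookah | None | No such aim is stated |

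**2. Was FMD recorded with charcoal?** The documents do not settle it.

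- The timing of FMD is given only in the e-hookah and ascorbic acid paragraphs.
- The charcoal paragraph lists no outcomes at all, so its silence on FMD proves nothing either way.
- The FMD methods mention possible shear differences across conditions without defining them. These could be pre/post, with or without ascorbic acid, or the two products.
- The endothelial section mentions nicotine and exhaled carbon monoxide. This does not help, because the ascorbic acid protocol also collected exposure biomarkers.

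**3. What separate pre/post tests would do if used as a product comparison (illustration).** Suppose the true effects are equal, the two tests are independent, and each has power p. The chance that exactly one is significant is 2p(1−p):

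- p = 0.5: 2 × 0.5 × 0.5 = 0.50
- p = 0.8: 2 × 0.8 × 0.2 = 0.32
- p = 0.9: 2 × 0.9 × 0.1 = 0.18

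This is a good reason not to draw a product conclusion from two p-values. The SAP does not propose to do so for FMD.

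**4. What the added contrast could deliver (illustration).** The unit is the SD of the pre-post change, r is the assumed between-session correlation, and the sequence groups have n1 and n2 participants (n = n1 + n2). With sequence in the model, the 95% half-width is

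t(0.975, n−2) × √[ (2(1−r)/4) × (1/n1 + 1/n2) ],

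which for equal groups reduces to t(0.975, n−2) × √(2(1−r)/n). At r = 0.5:

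- n = 10: 2.306 × √0.1 = 0.73
- n = 16: 2.145 × √0.0625 = 0.54
- n = 20: 2.101 × √0.05 = 0.47
- n = 30: 2.048 × √0.0333 = 0.37

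Over r from 0 to 0.7, the range is 1.03 to 0.56 at n = 10 and 0.53 to 0.29 at n = 30.

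**5. Cost of the sequence term.** Without it, the half-width is t(0.975, n−1) × √(2(1−r)/n).

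- Equal groups, n = 10, r = 0: 1.03 − 1.01 = 0.02 SD. With equal groups at n = 10 or more, the cost is about this or less.
- 12:4, n = 16, r = 0.5: 2.145 × √[0.25 × (1/12 + 1/4)] = 0.619, against 2.131 × 0.25 = 0.533. The cost is about 0.09 SD.
- 7:3, n = 10, r = 0.5: 2.306 × √[0.25 × (1/7 + 1/3)] = 0.796, against 2.262 × √0.1 = 0.715. The cost is about 0.08 SD.

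The sequence term is therefore nearly free only when the sequences are balanced.

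**6. Benefit of the sequence term.** In a simulation with 18 assumed participants, no product effect and a period effect of 1 SD on the difference in changes, the unadjusted test had a false-positive rate of 0.6% at 9:9 and 36% at 14:4. With sequence in the model, the rate was 4.6% to 5.2% across all settings run. The unadjusted product test in this comparison is not one that the SAP plans for FMD.

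**The case for a change.** The strongest case for acting is that the SAP leaves a reader unable to tell whether an FMD product contrast was impossible or simply not planned. If the data exist, the contrast needs no new participants or procedures and uses a model already in the SAP. Separate pre/post tests cannot stand in for it. A sequence term would also protect against serious error if the sequences were unequal.

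Much of this stands. The two sections do differ, the documents are silent on the point, and a product claim on FMD drawn from two p-values would be unsound. What does not follow is that the plan needs repair. The argument depends on FMD having been recorded with charcoal, which is unverified, and it guards against a claim that neither document makes.

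The addition is not free either. The SAP already reports which variables were non-normal, so any new contrast, and the choice of a rank method for shear-normalized FMD, would be made after the data were seen. Testing four dilation measures at 0.05 would carry up to 1 − 0.95⁴ = 18.5% chance of a false positive if they were independent. The true figure would be lower, since percent and absolute FMD come from the same diameters. That multiplicity would arise from the addition, not from the present plan.

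**Conclusion.** No change to the plan follows. Carried out as written, the endothelial-function analysis gives sound answers to the two FMD questions that the protocol asks. The absence of a product contrast for FMD is consistent with those aims, and its effect on the planned tests is nil.

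What remains is a gap in description: the documents do not say whether FMD was recorded in the charcoal session. A sensible analyst would fill it in one of two ways. If FMD was recorded only with e-hookah, no comparative FMD statement is possible. If it was recorded with both products, an estimate for percent FMD from the existing model, with sequence and a 95% interval, could be shown as exploratory and post hoc. Neither course alters the planned tests.

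The sizes above (a half-width of about 0.37 to 0.73 SD for 30 down to 10 participants at correlation 0.5, and a sequence-term cost from about 0.02 SD or less when balanced to about 0.09 SD at 12:4) rest on assumed inputs. They describe what an added analysis might offer and do not measure an error in this trial. The conclusion would change only if the trial made an FMD product claim based on within-session p-values, and the documents contain no such claim.

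### Does the ascorbic-acid comparison need a change because the SAP does not say when its 'pre' measurement was taken?

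*SAP*

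**What the plan says.** The SAP, under *Statistical Analysis Plan for Endothelial Function*, first gives the basic analysis: "we tested within-participant pre- versus post-exposure changes using paired t tests". The next comparison applies the paired t test to "compare the pre- versus post-changes induced by ascorbic acid versus e-hookah vaping" where the variable is normal, with the Wilcoxon signed-rank test for the rest. Neither change is defined further.

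The Protocol gives the purpose in *Study Protocol for Intravenous Ascorbic Acid Protocol*: "To determine if oxidative stress plays a mechanistic role in the e-hookah vaping-associated decline in FMD". It continues that "the acute effects of e-hookah vaping on FMD and exposure biomarkers were assessed before and after intravenous administration" of ascorbic acid. The regimen is a priming bolus "for 20 minutes followed by an intravenous infusion of 0.02 g per kg fat-free mass", the latter given over 60 minutes. The section does not place vaping, or the pre and post scans, within those 80 minutes.

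For vaping without ascorbic acid, the *E-Hookah Vaping Protocol* is explicit: "FMD were measured before and after (within ≤10 minutes) 30 minutes of e-hookah bowl vaping". On spacing, the Protocol says that "both exposure sessions were separated by a minimum of a 7-day washout period". That sentence concerns the e-hookah and charcoal sessions.

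**The concern.** Read alone, the SAP sentence seems to set a change caused by ascorbic acid against a change caused by vaping. Those are not like quantities, and their difference would not answer the mechanistic question. Read with the Protocol, it becomes the vaping change with ascorbic acid against the vaping change without it, which is sensible. One point then remains open: under ascorbic acid, was the starting value taken before the infusion or after it began but before vaping?

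This is the only comparison that addresses mechanism. If ascorbic acid raises resting flow-mediated dilation (FMD) by itself, a pre-infusion baseline would credit that rise as protection against vaping, even if the vaping effect were untouched. Order and spacing add a smaller worry. The stated washout is not given for the e-hookah assessments with and without ascorbic acid. If every participant had them in the same order, an order effect could not be told apart from the ascorbic-acid effect.

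**Working it through.** The documents give no sample size, SD, effect size or power for this comparison, so there is no design figure to reproduce. The check has four parts.

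**1. What the texts say about 'pre'.**
- *E-Hookah Vaping Protocol*: the acute effect of vaping on FMD is the change from before to after 30 minutes of vaping.
- *Intravenous Ascorbic Acid Protocol*: the thing assessed before and after the infusion is the acute effect of vaping, not resting FMD. Grammatically, the phrase labels two conditions, without and with ascorbic acid. It does not name a baseline scan.
- SAP: the sentence just before the comparison ties pre and post to exposure, and the Protocol uses exposure for the vaping and smoking sessions.
- Only the SAP's description of changes as induced by ascorbic acid points the other way.

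Three of the four indications favour a pre-vaping baseline in both conditions.

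**2. Timing.** Inputs are the Protocol's volumes and rates.
- Bolus: 100 mL / 5 mL per min = 20 min.
- Maintenance infusion: 30 mL / 0.5 mL per min = 60 min.
- Total: 20 + 60 = 80 min.

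Pre-to-post intervals, ignoring scanning and nitroglycerin testing, and assuming that the 10-minute limit on the post-vaping scan also holds under ascorbic acid:

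| Condition and baseline | Interval |
|---|---|
| Without ascorbic acid | 30 to 40 min |
| With it, pre-vaping baseline | 30 to 40 min |
| With it, pre-infusion baseline, vaping after the bolus | 20 + 30 = 50, to 60 min |
| With it, pre-infusion baseline, vaping after the full infusion | 80 + 30 = 110, to 120 min |

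The two baselines can therefore be distinct in time. A longer interval is not in itself a bias.

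**3. What each baseline estimates.** Let R0 and V0 be the resting and post-vaping values without ascorbic acid, with d = V0 − R0. With ascorbic acid, let the resting value be RA = R0 + b and the post-vaping value VA = RA + d + k. Here b is ascorbic acid's own effect on the resting value, and k is the amount by which it alters the vaping effect.
- Pre-vaping baseline: (VA − RA) − (V0 − R0) = k.
- Pre-infusion baseline: (VA − R0) − (V0 − R0) = k + b.

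The contrasts differ by exactly b and agree if b = 0. Only k answers the Protocol's question.

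**4. How much b could matter, by assumption only.** In units of the size of the vaping decline:

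| Assumed b | k = 0: pre-vaping | k = 0: pre-infusion | k = 0.50: pre-vaping | k = 0.50: pre-infusion |
|---|---|---|---|---|
| 0 | 0 | 0 | 0.50 | 0.50 |
| 0.10 | 0 | 0.10 | 0.50 | 0.60 |
| 0.25 | 0 | 0.25 | 0.50 | 0.75 |
| 0.50 | 0 | 0.50 | 0.50 | 1.00 |

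Rejection rate of a two-sided paired t test at 0.05 when k = 0 and the baseline is pre-infusion, from the noncentral t distribution with n − 1 degrees of freedom and noncentrality (b/SD) × √n, where SD is that of the paired difference:

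| Assumed n | b/SD = 0.25 | b/SD = 0.50 | b/SD = 0.75 |
|---|---|---|---|
| 10 | 10.9% | 29.3% | 56.2% |
| 20 | 18.6% | 56.5% | 88.9% |
| 30 | 26.3% | 75.4% | 97.8% |

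With a pre-vaping baseline the rate is 5% throughout. Every n and b in these two tables is assumed. They show what would follow from a pre-infusion baseline with a non-zero b; they are not evidence that either occurred.

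**The case for a change.** The strongest case for a change is that the baseline decides what the mechanistic comparison estimates, that the documents never state it, and that stating it would take about three sentences. The text even allows a third reading, in which the infusion follows vaping, so that the post-vaping scan is 'pre' and a later scan is 'post'. On this view the gap concerns the estimand and goes beyond wording.

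Part of this stands. No sentence gives the time of the starting measurement under ascorbic acid, and the spacing of the two e-hookah assessments is unstated. The algebra is correct, so a pre-infusion baseline would mix two effects. A report of the trial would be clearer for giving the scan times and the session order, and a common order would be a limitation to acknowledge.

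The rest does not carry. A sentence that admits several readings is a fault in the plan only if a sensible analyst would probably take a wrong one. Here the stated purpose concerns the decline that vaping causes, and the Protocol's own usage gives that effect a before-vaping start. The third reading fits poorly with a section that assesses the effect of vaping under two conditions. Defining the terms would record what was done; it would not alter the test, the data or the hypothesis.

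**Conclusion.** No change to the plan follows. The omission is real, but it is a gap that the surrounding text fills: take each participant's vaping change with ascorbic acid, subtract the vaping change without it, and apply the paired t or signed-rank test to the difference. That is the right contrast, and the SAP's choice of test suits it.

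The possible discrepancy equals b, ascorbic acid's effect on the resting value. The documents neither report b nor allow it to be bounded, and at b = 0 the two baselines give the same answer. The conclusion rests on reading pre and post as relative to vaping in both conditions, which the documents favour but do not state outright. If study records showed a pre-infusion baseline, the result would have to be read as k + b and not as protection alone. Nothing in the Protocol or SAP shows that this happened. The unstated order and spacing are likewise matters for the report and do not make the planned analysis wrong.

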Blood samples were obtained from the antecubital vein, drawn into pre-iced heparinized vacutainers, and placed on ice. Tubes were sent to the University of California, Los Angeles, Clinical Laboratory for inflammatory biomarker analyses, which were performed within 24 h after collection. One tube was centrifuged to separate plasma for antioxidant biomarker analyses, and samples were frozen at -80°C in a cryopreservative solution.

Arylesterase Activity: Activity was determined by the rate of hydrolysis of phenyl acetate to phenol. Briefly, 4 mL plasma was incubated with 3.5 mM phenyl acetate in 9 mM Tris-HCl buffer (pH, 8.0) containing 0.9 mM CaCl₂ at RT. The kinetics of phenol formation were determined by recording the absorbance at 270 nm every 15 s for 2 min. The activity was expressed as nanomoles of product formed per minute per milliliter of plasma.

PON-1 Activity: The ability of PON-1, associated with HDL, to hydrolyze paraoxon substrate was determined. The hydrolysis of paraoxon (diethyl-p-nitrophenyl phosphate) to p-nitrophenol by PON-1 was determined by incubating 5 mL of plasma with 1.0 mM paraoxon in 100 mM tris-HCl buffer (pH, 8.5). The kinetics of p-nitrophenol formation was determined by recording absorbance at 405 nm every 15 s for 4 min. The enzyme activity was expressed as micromoles of p-nitrophenol formed per minute for every 1 mL plasma and assayed in triplicates. The intra-assay CV for the assay was 2.60% and the interassay CV was 8.95%.

HDL Antioxidant Capacity: Capacity was determined as the ability of HDL to inhibit LDL-induced oxidation of dihydrodichlorofluorescein into the fluorescent dichlorofluorescein.

Capacity was expressed as an HDL oxidative index, determined by the ratio of dichlorofluorescein fluorescence in the presence and absence of HDL and assayed in triplicates. An index of < 1.0 denotes protective antioxidant HDL, whereas an index of > 1.0 indicates pro-oxidant HDL. The within-assay CV was 6.89%. The interassay CV for four separate measurements over a period of 2 months was 7.30%.

Serum hsCRP levels were analyzed using the immunoturbidimetric method using the Siemens Vista Dimension analyzer, which provides a minimum detection level of < 0.2 mg/L; and TNF α was analyzed using quantitative multiplex bead assay.

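### Does the product-by-time interaction lose precision, and so fall short as the primary contrast, because it does not adjust for each session's pre-exposure value?

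*SAP*

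**What the plan says.** The relevant text is the SAP section on central arterial stiffness and biomarkers of oxidative stress and inflammation. To compare the products, "we used a general linear model approach for repeated measures to examine differences between e-hookah and traditional combustible hookah". On the factors, "the models included two within-subject factors (product type and time point relative to exposure session"). Order of exposure is modelled too: "the sequence of type of product exposure was included as a between-group factor". One contrast is singled out: "The effect of primary interest was the interaction between the two within-subject factors, product type and time point relative to the exposure session". No baseline covariate is listed; the pre-exposure value enters as one level of the time factor.

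The same section says that paired t tests "were used to compare continuous variables between sessions before and after exposure". This can be read as pre against post within each session, or as one session against the other at each time point.

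On carryover, the Protocol section on the vaping and smoking exposure sessions says: "To mitigate the impact of carryover effects, both exposure sessions were separated by a minimum of a 7-day washout period". Neither document gives the number of participants, SDs, correlations or a planned effect for these outcomes, and neither says how the order of products was assigned.

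**The concern.** Each participant supplies a pre-exposure and a post-exposure value in both sessions. Let D_pre and D_post be the e-hookah minus charcoal-hookah differences within a participant. The interaction uses D_post − D_pre, which fixes the slope of D_post on D_pre at 1. If the paired t tests are read as session against session, they also test D_post alone, with the slope fixed at 0. On that reading the plan uses slopes of 0 and 1 and never estimates the slope.

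When the true slope is well below 1, subtracting all of D_pre adds noise. In a small crossover study this could widen the interval for the main effect and cost power, although the data for a regression adjustment are already in hand.

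**Working it through.** The plan gives no figure to reproduce. The checks below use assumed values: n = 18, r = corr(D_pre, D_post), and k = SD(D_pre)/SD(D_post). The true slope is then r/k. Effects are in SDs of D_post.

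**1. What the interaction is.** (E_post − E_pre) − (C_post − C_pre) = D_post − D_pre, where E is e-hookah and C is charcoal hookah. On a test data set, the repeated-measures interaction F and the squared t of the sequence-adjusted double difference were both 1.0542. The estimate matched a model with D_pre as an offset of slope 1 (−0.4195 for both). The change-score reading is correct.

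**2. Whether it is valid.** Averaged over the two sequences, a common period effect cancels. Carryover λ_E and λ_C leaves a mean D_pre of δ = (λ_C − λ_E)/2, so equal carryover leaves nothing. For any slope b, the bias of D_post − b·D_pre is δ_post − b·δ_pre. With no differential carryover it is zero for every b, including b = 1. In simulation both models were unbiased, with type I error of 4.7 to 5.3%.

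**3. How large the gain could be.** Variance ratio, planned to adjusted = (1 + k² − 2rk)/(1 − r²) × (n − 4)/(n − 3). At n = 18, k = 1, r = 0.3 this is 1.40/0.91 × 14/15 = 1.44.

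| | r = 0.3 | 0.5 | 0.7 | 0.9 |
|---|---|---|---|---|
| k = 1 | 1.44 | 1.24 | 1.10 | 0.98 |
| k = 0.7 | 1.10 | 0.98 | 0.93 | 1.13 |

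Values above 1 favour adjustment. At k = 0.7 and r = 0.7 the true slope is exactly 1, and adjustment only costs a degree of freedom.

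**4. Whether the documents locate the slope.** They do not. The only related figures are the assay CVs in the Protocol's biomarker section. If a session's pre and post samples share an assay run and the two sessions do not (the Protocol does not describe batching), the assay-only slope is 1 − (within CV)²/(between CV)².

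- PON-1: 1 − 2.60²/8.95² = 0.92, close to the planned slope of 1.
- HDL index: "The within-assay CV was 6.89"% and "The interassay CV for four separate measurements over a period of 2 months was 7.30"%. This gives 1 − 6.89²/7.30² = 0.11. The between-run figure comes from four measurements. With 3 df and normality its 95% interval is 4.1 to 27.2%, so the slope could be anything from 0 to 1 − 6.89²/27.2² = 0.94.

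**5. What adjustment costs under carryover.** Take k = 1 and δ = 0.3 SD, with r = 0.3/0.5/0.7.

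- Equal shift before and after exposure: the planned contrast has no bias and about 5% type I error. The adjusted bias is (1 − r)δ = 0.21/0.15/0.09 SD, with type I error of about 13/10/8%.
- Shift in the pre-exposure value only: the planned bias is −0.30 SD with type I error 17/22/34%. The adjusted bias is −rδ = −0.09/−0.15/−0.21 SD with about 6/10/20%.

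Neither analysis is better in both cases.

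**6. Whether the observed D_pre could settle the choice.** The 95% interval for mean D_pre has half-width t(0.975, 16)/√18 = 2.12/4.24 = 0.50 SD, and power to detect 0.3 SD is 22%. A significant D_pre would not say which analysis to trust. If it arose by chance, with no carryover, the planned contrast has type I error of roughly 22/17/12% among such trials, against 5% adjusted (separate simulation runs differ by one or two points). If it arose from carryover equal at both time points, the planned contrast is the unbiased one. Taking the smaller of the two p-values gives 7.9/7.4/6.9% even with no carryover.

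**The case for a change.** The strongest case for adjustment is that it needs no new data. It costs one residual degree of freedom and, without differential carryover, at most 1/(n − 4) more variance (1/14 = 7.1% at n = 18). At k = 1 and r = 0.3, power for an effect of 0.7 SD would rise from 0.65 to 0.81, and the mean interval width would fall from 1.16 to 0.98 SD. A precision gain can also survive some carryover: with δ = 0.3 SD the variance ratio is still about 1.30 at r = 0.3 and 1.13 at r = 0.5. Run beside the planned contrast as a labelled sensitivity analysis, it would leave the primary result untouched.

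The arithmetic stands, but it does not show that the plan is deficient. That gain belongs to one favourable corner of an assumed grid; at k = 0.7 and r = 0.3 power moves only from 0.77 to 0.80, and at r = 0.5 and 0.7 it falls by a point. A second model that neither replaces the planned contrast nor can be chosen on the observed baselines changes no conclusion, and it adds a p-value per outcome.

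The unstated method of assigning order is a real gap in the description. It does not undermine the contrast by itself, because averaging over sequences removes a common period effect however order was assigned. Only period effects that differ between the sequence groups would matter. Mean D_pre by sequence and an interval in native units would help a reader, but these are reporting details. The ambiguous paired t tests do not alter which effect the SAP names as primary.

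**Conclusion.** The concern does not hold. The interaction is a change-score contrast with the slope fixed at 1. It is a legitimate primary analysis for a two-product crossover with sequence in the model, and the 7-day minimum washout makes its carryover condition plausible without proving it. The condition is that differential carryover is absent, or equal before and after exposure.

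Regression on the pre-exposure difference is another defensible choice. At n = 18 its effect on variance runs from a clear gain (ratio 1.44) to a small loss (0.93), depending on correlations and SDs that the documents do not give. It trades that against bias when carryover persists through the session. All sizes rest on the assumed n, r, k and carryover. Not choosing this option is a matter of preference, not an error in the plan.
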